1.2.1 Clinical effectiveness and cost-effectiveness of exercise-based rehabilitation for LTCs

Exercise is a core component in the prevention of numerous chronic diseases and has been shown to be effective in the treatment of at least 26 LTCs. (26) Furthermore, there are convincing data describing the clinical effectiveness of structured exercise-based rehabilitation interventions in numerous LTCs, (10-15, 27) the structure and content of which are extremely consistent across high income countries, i.e., an 8-12 weeks course comprising a package of individually prescribed and progressed exercise to build fitness and strength, alongside a programme of multidisciplinary support to facilitate effective self-management, including but not limited to, symptom management, encouraging healthy lifestyle behaviours (e.g. smoking cessation, activity and diet) and managing mood disturbances. The rehabilitation intervention is preceded by a comprehensive assessment (this would cover as a minimum objective measure of functional capacity, HRQoL, symptom burden and mood disturbances). The duration of the intervention is principally based on the anticipated duration of exercise training to observe a physiological gain. (28) The data describes consistent improvements in HRQoL, symptoms, functional exercise capacity, anxiety and depression, activities of daily living, selfefficacy, and a reduction of symptoms. (17, 29). The primary outcome for these trials has typically been disease specific HRQoL (i.e. developed specifically for use in single disease groups) (30-32) or exercise capacity (commonly field walking tests, such as the minute walking test or incremental shuttle test). (33, 34)

A systematic review has confirmed there is evidence supporting the cost-effectiveness of CR for individuals but that the generalisability of study findings was limited due to the exclusion of patients with comorbidities as would typically be found in a real- world setting. (35) Comparable data exists for PR describing reductions in hospital admissions. (16) Exercise interventions for COPD have an estimated cost per quality-adjusted life year (QALY) of around £2-8k compared to inhaled drugs of between £7-187k per QALY. (18) The World Health Organisation have called for a global effort informed by their 'Rehabilitation 2030' policy (36) to

make rehabilitation accessible and affordable globally, recognising that it is necessary to keep people as independent as possible, and be economically productive. There is a misconception that rehabilitation is a luxury ("non-essential") service and is generally undervalued by health care systems.

1.3 Development of rehabilitation services for LTCs.

The most consistently provided services for people with LTCs is CR and PR, there remains poor provision of exercise based supervised rehabilitation programmes for other LTCs. In UK, PR and CR services are well developed and funded through current NHS commissioning arrangements (37). i.e. >200 PR and CR programmes (contributing to national audit programmes) with workforce training provided by national bodies to support the delivery of high-quality care (British Thoracic Society (BTS) and British Association for Cardiovascular Prevention and Rehabilitation (BACPR). However, there is currently no consistent provision of, or training for exercise-based rehabilitation programmes for other single LTCs. Some exceptions include isolated services developed for people with peripheral vascular disease, (38), arthritis (ESCAPE pain programme: Enabling Self-management and Coping with Arthritic Pain through Exercise a face-to-face group programme delivered in approximately 80 sites across the UK). (15) The structure and content of the programme delivered for arthritis is remarkably like CR and PR with a focus on supervised exercise and self-management, not surprisingly symptom management focusing on pain (as, for example compared to breathlessness) but will also include components addressing stress management, medication management and behaviours commensurate with a healthy lifestyle.

In recognition of this poor access to rehabilitation for people with multiple LTCs, the UK Chartered Society of Physiotherapy recently published the "RightoRehab" report/campaign. (39) This report identified that: "A radical modernisation is needed to ensure the quality and consistency of community rehabilitation services, offering an approach that is tailored to meet people's needs and priorities". In response to this report, in early 2020, the Chartered Society of Physiotherapy co-ordinated The Rehabilitation Alliance: a collaboration of 24 charities, trade unions, and professional bodies that have coalesced to lobby for equal access to high quality community rehabilitation services for all. The overarching aims of the Alliance are to:(1) develop a national strategy for quality rehabilitation, making it an essential component of healthcare, expand and modernise rehabilitation services to meet the scale of the need; (2) grow the multi-disciplinary workforce: (3) learn from the response to the COVID-19 pandemic on how to shape future rehabilitation needs; and (4) measure the need and impacts of rehabilitation. The Rehabilitation Alliance proposes that to meet these aims 'service disruption' is necessary to change the architecture of the current rehabilitation services.

1.4 Impact of rehabilitation programmes for LTCs

Accumulating co-morbidities compromises rehabilitation outcomes. (40) Although the precise reasons for this remain unclear, it may be reasonable to speculate that these programmes are designed specifically for a single disease and staff have expert knowledge and skill in that area but are less well equipped to managed other LTC's that may compromise the benefit of the programme to the individual. There has been some modest 'adaptations' (and little disruption) of services described in the literature. Research by the co-applicants describes accommodating patients with chronic heart failure into a conventional PR programme, acknowledging the lack of access for those with heart failure to a standard CR programme (41). A pilot RCT showed clinical outcomes to be consistent with CR programmes, (41). Arguably this project did not extend the scope but rather streamlined the service delivery and

thereby reduced the treatment burden for the individual. The scope of this programme has now extended to become a 'Breathlessness Rehabilitation Programme', which was acknowledged as an important innovation in the NHSE Long Term Plan (20). A feasibility trial has looked at extending the scope of CR services to participants post transient ischaemic attack and mild stroke. There were subtle changes in the structure of the programme reported but a much greater emphasis on workforce training and support. However, with appropriate training and support, this study showed that the integration of the new population into an existing service was both feasible and acceptable to all patient groups and staff. (42) These reports were not specifically focusing on those with multiple LTCs rather combining single disease cohorts.

We are aware of only two published reports to date that have assessed the impact of a structured rehabilitation programme for people with multiple LTCs: one small pilot trial (n=16) (43) and a single centre service evaluation (44). Whilst both studies support the feasibility of such rehabilitation provision and also indicate potential improvements in functional capacity, they are limited by their small sample size and single centre status. Furthermore, given their feasibility/pilot design, neither of these two studies informs what should be the appropriate primary outcome for a trial of rehabilitation for people with multiple LTCs. A consensus event was undertaken by co-applicants (RE/SS) to explore suitable outcomes for a combined rehabilitation programme for COPD and chronic heart failure. (45) Both clinicians and patients proposed that the most appropriate measure for either research or a clinical service was HRQoL but stopped short of identifying a preferred measure. A Delphi panel co-ordinated by one of the co-applicants (SuS) including 26 experts from 13 countries aimed to develop a consensus-based list of core outcome measures within multimorbidity research. This Delphi exercise also found HRQoL to be the highest scored outcome alongside mental health outcomes, and mortality. (46) A recent systematic review explored treatment priorities of those living with LTC's and compared to the priorities considered important by clinicians that would inform their treatment decisions. (47) Although the included studies and trial data were highly heterogenous, this review showed that for patients their consistent preference towards 'maintaining independence', 'staying alive', 'pain relief' and 'symptom relief'. The authors concluded that preserving functional ability as a key priority for patients living with LTCs. Besides this limited investigator driven research for people with multiple LTCs we could find no reports of rehabilitation specifically for people with multiple LTCs but did find reports of PR services beginning to accept those with heart failure on social media.

Overall, the single-disease framework by which most health care and workforce training is provided is arguably not fit for the challenge of individuals with multiple LTCs. Indeed, a landmark paper in the Lancet on multimorbidity concluded that a 'complementary strategy is needed, supporting generalist clinicians to provide personalised, comprehensive continuity of care' (3). This can feasibly be extrapolated to call for a comprehensive rehabilitation strategy for people with multiple LTCs

2. RESEARCH QUESTION /OBJECTIVES AND OUTCOME MEASURES/ENDPOINTS

The overarching aim of the Personalised Exercise Rehabilitation FOR people with Multiple LTCs (PERFORM) research programme is to better understand the impact of living with multiple LTCs and develop and evaluate a rehabilitation intervention for this population. Our PERFORM programme consists of five linked work packages (WPs)

WP1: Identifying people with multiple LTCs likely to benefit from rehabilitation

WP2: Intervention development/workforce planning

WP3: Feasibility study for full RCT with embedded process evaluation and health economic evaluation

WP4: Multicentre RCT and prospective cohort study

WP5: Role of Social Media within mutlicentre RCT

This protocol document refers to WP3 - PERFORM Feasibility Study

2.1 Primary Objective

2.1.1 Aim

To implement the PERFORM intervention across three sites and assess the feasibility and acceptability of the PERFORM intervention and study methods and assess whether progression criteria are achieved and a full trial (WP4) is warranted.

2.1.2 Objectives

- To assess study recruitment and retention.
- To assess the feasibility, acceptability of the intervention exploring barriers and facilitators, to uptake and engagement from both participant and healthcare provider perspectives.
- To assess fidelity and reach of the intervention.
- To further refine the intervention and programme theory.
- To assess the feasibility and acceptability of data collection tools.
- To obtain estimates of key cost drivers.
- To assess risks of bias/contamination.
 - D: Design randomised controlled trial
 - P: Population People with mutiple long-term conditions (mutlimorbidity)
 - I: Intervention PERFORM intervention + usual care
 - C: Control usual care alone
 - O: Outcome(s) feasibility and acceptability of the PERFORM intervention and study methods
 - T: Time baseline (pre-randomisation) and 3-months post-randomisation

2.2 Outcome Measures

The primary outcome of this feasibility study will be to assess whether pre-specified progression criteria are met to progress to the full randomised trial to assess clinical and cost-effectiveness of the PERFORM intervention (WP4). Progression criteria will be agreed with the Programme Steering Committee at the start of study. Our funded application proposed criteria based on recruitment, retention, and intervention adherence (session attendance) and engagement from clinician reports and patient self-reports (see Table below).

| | | Red | Amber | Green |
|---|-------------------|---|---|---|
| Recruitment | | <75% | 75-99% | 100% |
| % of N=60 pati | ent target in 4.5 | | | |
| months | | | | |
| Retention at 3 months (% of patients with complete EQ-5D data at 3 month follow up) | | <65% | 65-79% | 80-100% |
| Intervention adherence | Attendance | <40% of patients attend ≥ 60% of sessions | <50% of patients attend ≥ 60% of sessions | 60%-100% of patients attend ≥ 60% of sessions |

Red: Do not progress to the main trial

Amber: Progress if action plan to mitigate problems can be determined and agreed with the

Programme Steering Committee.

Green: Progress directly to the main trial.

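### The adherence progression row assigns no category to 50% to <60%, so results just below Green have no pre-specified decision

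*Protocol*

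**What the plan says.** Protocol Section 2.2 makes the primary outcome of this feasibility study whether the progression criteria are met, and sets out a Red/Amber/Green table. The adherence row reads:

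- Red: "<40% of patients attend ≥ 60% of sessions"
- Amber, then Green: "<50% of patients attend ≥ 60% of sessions | 60%-100% of patients attend ≥ 60% of sessions"

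The consequences are printed under the table: "Red: Do not progress to the main trial"; "Amber: Progress if action plan to mitigate problems can be determined and agreed with the" PSC; and "Green: Progress directly to the main trial".

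The other two rows run without a break in whole percentages: recruitment <75 / 75–99 / 100 and retention <65 / 65–79 / 80–100.

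Section 2.3 names adherence as one of three co-primary outcomes because it belongs to the progression criteria. Section 10.2.2 reports it as a number and percentage with a 95% confidence interval. Neither section, nor the Trial Summary, gives other bands. Section 2.2 also says that the criteria are to be settled with the PSC when the study begins, and that the table is what the funded application put forward. The sentence introducing the table names "intervention adherence (session attendance) and engagement from clinician reports and patient self-reports (see Table below"), but the table has no engagement row.

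**The concern.** A traffic-light rule should give every possible result exactly one colour. This row does not. Between the end of Amber (just under 50%) and the start of Green (60%) there is a band ten percentage points wide with no colour and therefore no stated consequence.

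If the observed adherence falls there, the primary question has no pre-specified answer on this criterion. It could be treated as Amber, which makes progression conditional on an agreed action plan, or as Green, which does not. Attendance is taken on registers at every session (Section 2.4.6), so it becomes known as the study runs. A band settled late could be settled by people who already know roughly where the result lies.

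**Working it through.** **Inputs**

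- Intervention arm: 60 × 2/3 = 40 patients, which reproduces the 40 in Sections 3 and 10.1.
- Bands: Red <40%, Amber <50%, Green 60–100% (Section 2.2).
- Expected true adherence *p*: not stated in the protocol. A range of 40% to 70% is assumed here for illustration.

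The protocol gives no calculation for the adherence bands, so there is no figure of its own to reproduce beyond the arm size.

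**Step 1: apply the printed cells to every count out of 40.**

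| Adherent patients | Percentage | Cells met as printed |
|---|---|---|
| 0–15 | 0–37.5 | Red and Amber |
| 16–19 | 40–47.5 | Amber |
| 20–23 | 50–57.5 | none |
| 24–40 | 60–100 | Green |

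Eight counts (16–23) lie between Red and Green, and four of them have no category. The same gap appears in smaller arms: 15–17 of 30 and 18–21 of 36.

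**Step 2: check the other rows at N = 60.** Recruitment: 44/60 = 73.3% is Red, 45/60 = 75% is Amber, 59/60 = 98.3% is Amber and 60/60 is Green. Retention: 38/60 = 63.3% is Red, 39/60 = 65% is Amber, 47/60 = 78.3% is Amber and 48/60 = 80% is Green. No count is left out.

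**Step 3: chance of landing in the gap.** With X ~ Binomial(40, *p*),

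P(gap) = Σ C(40, x) pˣ (1 − p)⁴⁰⁻ˣ, summed over x = 20 to 23.

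At *p* = 0.50 the four terms are 0.1254 + 0.1194 + 0.1031 + 0.0807 = 0.429. Over the assumed range:

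| True adherence | 40% | 45% | 50% | 55% | 60% | 65% | 70% |
|---|---|---|---|---|---|---|---|
| P(no category) | 0.12 | 0.28 | 0.43 | 0.47 | 0.36 | 0.19 | 0.06 |

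**Step 4: try to resolve the row by reading order.** Taking Red before Amber gives an implied Amber of 40% to <50%, and the overlap disappears. The range 50% to <60% still meets no cell, whichever order is used.

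**Step 5: close the gap.** With Red <40% and Green ≥60% kept, Amber becomes 40% to <60%: Red 0–15, Amber 16–23, Green 24–40, with each count classified once. If Green instead started at 50%, counts 20–23 would be Green. The two repairs lead to different consequences for the same result.

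**The case against.** Several things can fairly be said on the other side.

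- **The criteria are still to be agreed.** Section 2.2 provides for agreement with the PSC at study start, so there is a planned moment before data at which the cell can be corrected. This stands: a decision made after seeing the data is a risk, not a certainty. It does not cure the printed table, because agreeing the table as it is would carry the gap forward.
- **The gap is not at the stopping boundary.** This also stands. It lies between Amber and Green, both of which allow progression. What is undefined is whether an agreed action plan must come first.
- **The overlap is only formal.** A reader might infer that below 40% the plan gives two contradictory answers. That is literally so, but in an ordered scale Red is naturally taken first, and the contradiction goes.
- **Amber is obviously meant to be 40–59%.** That fits the pattern of the other rows but is stated nowhere. The document does not show which cut-point is wrong.
- **The other rows are not perfect either.** They are complete at N = 60 or in whole percentages. With 58 randomised, 46/58 = 79.3% retained would fall between the printed Amber and Green. That is a rounding matter, far smaller than a ten-point gap.

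A reader might also take engagement to be a fourth criterion whose thresholds were left out. The documents do not support this: the Trial Summary, the table and Section 2.3 all list the same three criteria (recruitment, retention and attendance). The word in the introductory sentence appears to be a leftover.

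**Conclusion.** The point holds as an internal specification error. Adherence of 50% to <60%, or 20–23 of 40 patients, has no category, and nothing elsewhere in the protocol supplies one. Because adherence is a co-primary progression criterion, the plan does not pre-specify whether results just below Green need an action plan before the main trial. Amber's missing lower bound is a lesser fault in the same cell.

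The chance of meeting the gap runs from 0.06 to 0.47 over assumed true adherence of 40% to 70%, with the largest values at 50–55%. These figures assume exactly 40 patients and independent attendance. Sessions are delivered in groups, so attendance may be correlated and the probabilities are indicative only. A reader might infer that the gap covers the most plausible results. That cannot be claimed, since no expected adherence is stated and the chance is small towards either end of the range. The classification gap itself depends on none of these assumptions.

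**What to change.** Rewrite the adherence row so that the three bands cover every value once. If the printed Red and Green limits are kept, Amber becomes 40% to <60% of patients attending at least 60% of sessions (16–23 of 40), in line with the other rows. The sponsor and PSC should confirm that these are the intended cut-points at the agreement already planned for study start, and in any case before attendance data are seen.

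As a minor tidy-up, remove engagement from the sentence introducing the table.

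The cost is one table cell, one phrase and a PSC confirmation that is already foreseen. No change to sample size, data collection or analysis is needed.

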2.3 Definition of co-primary feasibility outcome(s)

The following outcomes will be co-primary outcomes as they all form part of the progression criteria:

- Proportion of recruitment target recruited, calculated as percentage recruitment target (60 participants) at end of 4.5 months recruitment period
- Retention at 3 months, calculated as the percentage of patients randomised with complete EQ-5D data at 3 months follow up.
- For patients randomised to the PERFORM intervention: proportion of patients achieving ≥60% of sessions attended at end of intervention^a
- ^a Proportion of sessions attended will be calculated from the number of sessions attended out of the scheduled 12 sessions.

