2.4.4 Further refine the intervention and programme theory

This will be completed at end of WP3 using data primarily from the process evaluation.

2.4.5 Feasibility and acceptability of data collection tools:

The proportion of 60 feasibility study patients with complete outcome data at 3-month follow up. Information on perceived outcome completion burden will be collected in patients interviews (see process evaluation, section 9).

2.4.6 Feasibility, acceptability of the intervention exploring barriers and facilitators to uptake and engagement from both participant and healthcare provider perspectives.

This will be assessed through qualitative interviews with patients and PERFORM intervention providers – see process evaluation section. This will also be assessed based on the adherence to the intervention (i.e. number of sessions attended out of the intervention program); adherence will be measured for each individual participant, which will be collected using attendance registers taken at each exercise session.

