7. INTERVENTION & CONTROL

7.1 Intervention group

The PERFORM rehabilitation programme will comprise an 8 week supervised rehabilitation programme, 6 weeks, twice weekly then 2 weeks, once a week that will be offered in either a primary or secondary care setting. Each session will last for 2 hours (1hr of 'move and improve

exercise sessions, and 1hr patient 'Health and Wellbeing' self care support session and Q&A/opportunity to interact with the group). The intervention will be offered within 4 weeks of randomisation.

The rehabilitation programme will comprise an exercise component with an accompanying education programme. The 'Health and Wellbeing' self care support sessions / educational package will offer advice and support for behaviour change to support positive lifestyle changes and symptom management. Much of the advice will be appropriate to all participants for example health eating, the benefits of exercise, stress management and relaxation techniques, medicines adherence, and exacerbation of symptoms. The aim of the education 'health and wellbeing' package is to support symptom management, risk factor management and enhance self-management skills. The education programme will be delivered by healthcare professionals delivered as informal and interactive sessions. The information will be supplemented by written leaflets and material to support the individual to share with their family and carers. After the 8 week programme the participant will have a discharge appointment in most cases this will take place 1-2 weeks following the last rehabilitation session.

Each 'move and improve' exercise session will offer an individually prescribed and progressed aerobic walking programme (a combination of walking (treadmill where available). In addition resistance training will be delivered that will be individually prescribed and progressed.

Participants will also be encouraged to complete a home exercise programme that will be closely monitored. A home exercise booklet will be provided as well as a progress tracker standardised exercise diary that will ask participants to record exercise frequency, duration and symptom scores post bout of exercise. This will be recorded for the aerobic and resistance programme.

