Participants are then invited to take part in 2 further group maintenance sessions, one 4 months after randomisation and one 6 months after randomisation, this will give participants the opportunity to review their long-term progress and address any further questions. After these visits the participant will return to their usual care.

There is no national benchmarking for staff to participant ratio, but we will take guidance from the pulmonary and cardiac rehabilitation standards recommending a minimum of 1:8 ratio, with a minimum of two healthcare professionals in any session.

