10. DATA ANALYSIS

10.1 Sample size calculation

In order to achieve the feasibility objectives (see above) of this feasibility study, a total of 60 patients will be recruited over 4.5 months. Given we are interested in the acceptability of the intervention, for efficiency, we will randomise 40 participants to the intervention group and 20 to the control group. We anticipate a loss to follow up of 20% at 3-months.

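### The co-primary adherence outcome divides by 12 sessions, but the programme in section 7.1 has 14, so the 60% attendance cut is 8 or 9 sessions depending on which section is followed

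*Protocol*

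**What the plan says.** Section 2.3 lists adherence among the three co-primary outcomes, as the "proportion of patients achieving ≥60% of sessions attended at end of intervention". Its footnote fixes the denominator: "Proportion of sessions attended will be calculated from the number of sessions attended out of the scheduled 12 sessions".

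Section 7.1 is the only description of the supervised schedule: an "8 week supervised rehabilitation programme, 6 weeks, twice weekly then 2 weeks, once a week". It then adds the maintenance contacts: "Participants are then invited to take part in 2 further group maintenance sessions, one 4 months after randomisation and one 6 months after randomisation".

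Section 2.4.6 also describes adherence, as the "number of sessions attended out of the intervention program", with a register taken at every exercise session. It gives no number.

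In the section 2.2 table, Green for adherence is "60%-100% of patients attend ≥ 60% of sessions". Section 10.1 sets the size of the group: "we will randomise 40 participants to the intervention group and 20 to the control group". Section 10.2.2 repeats the 60% cut without a denominator and adds a median and interquartile range of the percentage of sessions attended.

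**The concern.** The footnote in section 2.3 presents 12 as the scheduled number of sessions, but the schedule in section 7.1 adds up to 14. The only count that gives 12 leaves out the two once-weekly sessions, and the protocol nowhere says that they are left out.

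The footnote can then be applied in two ways:

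- **Reading A:** every attended session counts, divided by 12.
- **Reading B:** only 12 of the sessions, such as the twice-weekly block, count in both numerator and denominator.

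Neither agrees with attendance measured over the whole 8-week programme. Adherence is one of three criteria that decide whether the main trial goes ahead, and its cut should not be open to choice once the registers have been seen. Two other rules are affected. Under Reading A, full attendance scores 14/12 = 117%, so the summary in section 10.2.2 could exceed 100%. Section 10.7 treats unresolved missing attendance as non-attendance, which cannot be applied until it is settled which sessions are in scope.

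**Working it through.** **Session count (section 7.1).** 6 weeks × 2 + 2 weeks × 1 = 14. The section 2.3 figure of 12 is reproduced only by the twice-weekly block, 6 × 2 = 12. Adding the two maintenance sessions gives 16.

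**Cut for at least 60%.** The smallest whole number not below 0.6 × n:

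- n = 12: 7.2, so 8 sessions (8/12 = 66.7%)
- n = 14: 8.4, so 9 sessions (9/14 = 64.3%)

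**Who is classified differently, compared with at least 9 of 14.**

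- Reading A: a patient attending 8 of 14 (57.1%) scores 8/12 = 66.7% and counts as adherent.
- Reading B, with the first 12 sessions as the block: 7 of the first 12 plus both weekly sessions is 9/14 = 64.3%, but scores 7/12 = 58.3% and fails. Conversely, 8 of the first 12 and neither weekly session is 8/14 = 57.1%, but scores 66.7% and passes.

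**Green line.** 0.6 × 40 = 24 intervention patients.

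**Size.** The protocol gives no attendance distribution, so these inputs are assumptions: mean attendance m from 55% to 80%, within-person correlation r of 0.2, 0.4 or 0.6, and a beta-binomial model over 14 sessions with a = m(1 − r)/r and b = (1 − m)(1 − r)/r. Then:

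- A minus reference = P(exactly 8 of 14)
- B minus reference = P(8 of first 12, 0 of last 2) − P(7 of first 12, 2 of last 2)

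Differences in percentage points, for r = 0.2 / 0.4 / 0.6:

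| Mean attendance | A minus reference | B minus reference |
|---|---|---|
| 55% | 9.5 / 5.7 / 3.4 | −2.2 / −1.4 / −0.8 |
| 60% | 9.4 / 5.6 / 3.3 | −2.3 / −1.4 / −0.8 |
| 65% | 8.8 / 5.3 / 3.1 | −2.4 / −1.4 / −0.8 |
| 70% | 7.9 / 4.9 / 2.9 | −2.3 / −1.3 / −0.8 |
| 75% | 6.6 / 4.3 / 2.6 | −2.1 / −1.2 / −0.7 |
| 80% | 5.2 / 3.6 / 2.2 | −1.8 / −1.1 / −0.6 |

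In patients out of 40, A adds 0.022 × 40 = 0.9 to 0.095 × 40 = 3.8. B removes a net 0.006 × 40 = 0.2 to 0.024 × 40 = 1.0. The two readings differ from each other by 2.8 to 11.7 points.

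**Crossings of the 60% line in the 18 cases.**

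- Reading A, one: m = 60%, r = 0.2, where 51.9% becomes 61.2%.
- Reading B, two: m = 65%, where 60.1% becomes 57.7% (r = 0.2) and 60.3% becomes 58.9% (r = 0.4).

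**The case against.** The conflict between sections 2.3 and 7.1 is not in dispute; the objections concern its size and which number is right.

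- **Reading A is the less natural one.** A count out of 12 suggests that the attended sessions come from those 12, and a score of 117% looks unintended. Without A, the net effect is at most 1 patient in 40. This is fair, and it is why the readings are reported separately. The footnote does not exclude A, though, and B depends on a block of 12 that the protocol never identifies.
- **The crossings are fragile.** Only 3 of 36 comparisons cross 60%, and under B the reference value is already on the line. The sampling error at 60% with 40 patients is √(0.6 × 0.4/40) = 7.7 points, well above B's shifts. This stands, and it limits the point to results near the boundary.
- **Losing Green need not stop the trial.** In all three crossings the non-Green value lies between 50% and 60%, a range to which the section 2.2 table gives no colour. If it were treated as Amber, progression would still be possible with an agreed action plan. This stands; the gap in the table is a separate matter.
- **Section 2.4.6 gives no number** and fits either count. This is correct: the contradiction is between 2.3 and 7.1.
- **Fourteen may not be the right number.** Appendix 1 records that version 2.0 amended the rehabilitation schedule, but the earlier schedule is not shown. If 12 is the true schedule, the cut is 8 of 12 and nobody is misclassified. This also stands, so the fix has to allow for either correction.
- **There are later safeguards.** The steering committee agrees the criteria at the start, and the SAP is finalised before data lock. Both could settle the matter, but neither removes the contradiction from the protocol.

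**Conclusion.** The concern holds. Section 2.3 states 12 scheduled sessions, section 7.1 schedules 14, and both are current text. The cut for a co-primary progression criterion is therefore 8 or 9 sessions depending on the section followed. If 14 is right, the effect compared with 9 of 14 is an increase of 2.2 to 9.5 points under Reading A (about 1 to 4 of 40 patients) or a net decrease of 0.6 to 2.4 points under Reading B (at most 1 of 40). These sizes rest on the assumed means, correlations and beta-binomial model; the session counts and the two cuts do not. The point should be fixed, but it would change a decision only close to a boundary.

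**What to change.** Establish which schedule is intended, before attendance data are examined, and then make one of two corrections:

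- If 14 sessions are delivered, replace 12 with 14 supervised sessions in section 2.3. State that adherent means at least 9 of 14 and that the 4- and 6-month maintenance sessions are not counted.
- If the programme really has 12 sessions, correct the weekly pattern in section 7.1. State in section 2.3 that adherent means at least 8 of 12, again without the maintenance sessions.

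Give the same number in section 2.4.6, so that the register-based measure and the co-primary outcome agree.

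The cost is wording only. If all attended sessions were going to be counted over 12, moving to 9 of 14 makes the adherence figure slightly less favourable.
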